4.3 Withdrawal of Subjects from Study Treatment and/or Study

Permanent discontinuation of Durvalumab

An individual subject will not receive any further investigational product if any of the following occur in the subject in question:

1. Withdrawal of consent or lost to follow-up
2. Adverse event that, in the opinion of the investigator or the sponsor, contraindicates further dosing. Patients with grade 3 toxicity at least possibly related to study drug will discontinue durvalumab. Patients with prolonged grade 2 toxicity or who require dose delays for more than 2 weeks or require prolonged steroid use will discontinue durvalumab.
3. Subject is determined to have met one or more of the exclusion criteria for study participation at study entry and continuing investigational therapy might constitute a safety risk
4. Pregnancy or intent to become pregnant
5. Any AE that meets criteria for discontinuation as defined in Appendix A
6. Grade ≥ 3 infusion reaction
7. Subject noncompliance that, in the opinion of the investigator or sponsor, warrants withdrawal; eg, refusal to adhere to scheduled visits
8. Initiation of alternative anticancer therapy including another investigational agent
9. Confirmation of PD and investigator determination that the subject is no longer benefiting from treatment with durvalumab

Subjects who are permanently discontinued from further receipt of investigational product, regardless of the reason (withdrawal of consent, due to an AE, other), will be identified as having permanently discontinued treatment.

Subjects who are permanently discontinued from receiving investigational product will be followed for safety per Section 10.3.1 and Appendix C or D, including the collection of any protocol-specified blood specimens, unless consent is withdrawn or the subject is lost to

Clinical Study Protocol

Drug Substance Durvalumab (Medi4736)

Study Number MCC 18788/MCC18788/ESR-15-11326

Edition Number 1.9.4

Date 10/08/2018

follow-up or enrolled I another clinical study. All subjects will be followed for survival. Subjects who decline to return to the site for evaluations will be offered follow-up by phone every 3 months as an alternative.

Withdrawal of consent

If consent is withdrawn, the subject will not receive any further investigational product or further study observation.

4.4 Replacement of subjects

Subjects withdrawn from the study prior to the month 6 /week 26 mapping biopsy will be replaced to ensure total of 34 evaluable subjects. Subjects who are incorrectly enrolled but are not yet initiated on treatment should be withdrawn from the study and replaced.

5. INVESTIGATIONAL PRODUCT(S)

5.1 Durvalumab

The Investigational Products Supply section of AstraZeneca/MedImmune will supply durvalumab to the investigator as a 500-mg vial solution for infusion after dilution.

5.1.1 Formulation/packaging/storage

Durvalumab will be supplied by AstraZeneca as a 500-mg vial solution for infusion after dilution. The solution contains 50 mg/mL durvalumab, 26 mM histidine/histidine-hydrochloride, 275 mM trehalose dihydrate, and 0.02% (weight/volume) polysorbate 80; it has a pH of 6.0. The nominal fill volume is 10 mL. Investigational product vials are stored at 2°C to 8°C (36°F to 46°F) and must not be frozen. Durvalumab must be used within the individually assigned expiry date on the label.

5.1.2 Durvalumab Doses and treatment regimens

Treatment with fixed dose durvalumab at 1500 mg Q4W durvalumab (equivalent to 20 mg/kg Q4W, based on an average body WT of 75 kg) commences on Day 1 following confirmation of eligibility into the study and continues on a Q4W schedule for a maximum duration of treatment of 12 months (maximum of 13 doses). Study treatment should be discontinued prior to 12 months if there is confirmed PD (unless the investigator considers the subject to continue to receive benefit from treatment), initiation of alternative cancer therapy,

unacceptable toxicity, withdrawal of consent, or if other reasons to discontinue study treatment occur.

Subjects who have a dose interruption due to toxicity at any point in the first 12 months of treatment may resume treatment and complete the 12-month treatment period.

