- Compare the tumor mutation burden and alterations in DNA repair genes in the pre and post Durvalumab urothelial bladder cancer samples

Study Design:

This is a multicenter, open-label, Phase 2 study of Durvalumab to evaluate its antitumor activity for BCG refractory urothelial carcinoma in situ (CIS) of the bladder. Durvalumab will be given every 4 weeks at 1500 mg IV for total of 12 months. Cystoscopy with biopsy and TURBT (if indicated) will be performed at baseline, and every 3 months during the 12 months treatment period and then every 4 months in the 12 month surveillance period. Of note, cystoscopy at baseline, month 6, and 24 will be performed in the operating room with mapping biopsies. Patients will be off study if any of the biopsies document muscle invasive (T2 or above) urothelial carcinoma. Patients will also be off study if their month 6, 12, 16, 20, biopsies show persistent (month 6) or recurrent CIS or invasive (T1 or above) urothelial carcinoma. Otherwise, patients will remain on study until after the month 24 biopsy.

Number of Centers: 2-3 centers in North America

Number of Subjects: 34

Study Population:

Adult male or female subjects with pathologically confirmed urothelial carcinoma in situ (CIS) of the bladder that is refractory to BCG (see inclusion criteria 2).

Inclusion Criteria:

1. Age \geq 18 years at the time of screening with life expectancy of \geq 2 years
2. Must have pathologically confirmed urothelial carcinoma in situ (CIS) of the bladder that meet one of the following criteria:
 1. Persistence of high-grade CIS at 6 months following an adequate course of BCG; OR
 2. Stage/grade progression at 3 months after induction BCG; OR
 3. Recurrence of high-grade CIS after achieving a disease-free state (i.e., CR) following induction of an adequate course of BCG that occurs $<$ 9 months after the last exposure to BCG; OR
 4. Persistent CIS noted on the bladder biopsies within 3 months of completing at least 2 induction BCG (minimum of five weekly instillations).
- An adequate course of BCG should be defined as at least one course of induction (minimum of five weekly instillations) and one maintenance (two of three instillations) in a 6 months period, with an exception for any patient with grade/stage progression after induction BCG (minimum of five weekly instillations).
3. ECOG performance status of 0-1.

4. Adequate organ and marrow function, as defined as:

- Hemoglobin ≥ 9.0 g/dL,

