Sample Size Determination: The null hypothesis is the 18% historical complete response rate at month 6 will be tested against a one-sided alternative of 40% or higher complete response rate with Durvalumab at month 6 in BCG refractory CIS of bladder. We use a Simon's two-stage design (Simon, 1989) based on the optimal two-stage designs and admissible designs (Jung et al. 2004) for Phase II single arm clinical trials. The required total number of subjects is 34. 13 is the number of subjects accrued during stage 1. If 3 or fewer responses are observed during stage 1, the trial is stopped early for futility. If 9 or fewer responses of total 34 patients are observed by the end of stage two, then no further investigation of the drug is warranted. This design yields a one-sided type I error rate of 0.047 and power of 80% when the true response rate is 40% based on Simon's optimal two-stage design.

SCHEDULE OF STUDY ASSESSMENTS**Schedule of study assessments: Screening and Treatment Period (<<12 months: maximum of 13 doses, last infusion week 50>>)**

Assessments to be performed at the times stipulated in the table and as clinically required in the management of the subject.	Screening	All assessments to be performed pre-infusion unless stated otherwise				
		Baseline	Every 4 weeks	Every 3 months of 12 months treatment phase	Every 4 months of the 12 months surveillance phase	End of Trial visit
Day	-28 to -1	1	Day 1 of the week			
Week	-4 to -1	0	4, 8, 12, 16, 20, 24, 28, 32, 36, 40, 44, 48, (± 3 days)	14, 26, 38, 52 (± 14 days)	68, 86 104, (±14 days)	105 (±7 days)
Written informed consent/assignment of subject identification number	X					
Demography and history of tobacco and alcohol use	X					
Previous treatments for CIS of bladder	X					
Formal verification of eligibility criteria	X					
Hepatitis B and C; HIV	X					
Urine hCG or serum βhCG ^b	X	As clinically indicated				
Durvalumab administration		X	X			
Clinic visit with history and physical examination ^c	X	X	X		X	X

Schedule of study assessments: Screening and Treatment Period (<<12 months: maximum of 13 doses, last infusion week 50>>)

Assessments to be performed at the times stipulated in the table and as clinically required in the management of the subject.	Screening	All assessments to be performed pre-infusion unless stated otherwise					
		Baseline	Every 4 weeks	Every 3 months of 12 months treatment phase	Every 4 months of the 12 months surveillance phase	End of Trial visit	

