3. STUDY DESIGN

3.1 Overview of study design

This is a multicenter, open-label, Phase 2 study of Durvalumab to evaluate its antitumor activity for BCG refractory urothelial carcinoma in situ (CIS) of the bladder. We use a Simon's two-stage design (Simon, 1989) based on the optimal two-stage designs and admissible designs (Jung et al. 2004) for Phase II single arm clinical trials. In the first stage of this study plan, 13 patients will be accrued. If there are 3 or fewer responses in these 13 patients, the study will be stopped. Otherwise, 21 additional patients will be accrued for a total of 34. Durvalumab will be given every 4 weeks at 1500 mg IV for total of 12 months/13 doses. Cystoscopy with mapping biopsy and TURBT (if indicated) will be performed at

Clinical Study Protocol

Investigational Drug Substance: MEDI4736 Durvalumab (Medi4736)

Study Number MCC 18788/MCC18788/ESR-15-11326

Edition Number 1.9.4

Date 10/08/2018

baseline, month 6, and 24. Urine cytology with UroVysion test will be performed at baseline, month 6, and 24. Patients will be off study if any of the biopsies documented muscle invasive (T2 or above) urothelial carcinoma. Patients will also be off study if their month 6, 12, 18 biopsies showed persistent (month 6) or recurrent CIS or invasive (T1 or above) urothelial carcinoma. Otherwise, patient will remain on study until after the month 24 biopsy.

Historical controls will be used to assess the efficacy of Durvalumab. For exploratory analysis on PD-L1 expression, PD-L1 IHC will be performed with the SP263 antibody developed by Ventana. IHC positivity (either on tumor cells and/or infiltrating immune cells) will be assessed on the available mapping biopsy and or TURBT samples at time points defined in SCHEDULE OF STUDY ASSESSMENT.

Data Monitoring Committee (DMC) at Moffitt Cancer Center will monitor this phase 2 study initiated by Moffitt's investigator.

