9. DISEASE EVALUATION AND METHODS

The response to immunotherapy may differ from the typical responses observed with cytotoxic chemotherapy including the following (Wolchok et al 2009, Nishino et al 2013):

- Response to immunotherapy may be delayed
- Response to immunotherapy may occur after PD by conventional criteria
- The appearance of new lesions may not represent PD with immunotherapy
- SD while on immunotherapy may be durable and represent clinical benefit.

Based on the above-described unique response to immunotherapy, subjects with persistent CIS at the month 3 bladder biopsy will continue to receive Durvalumab until the month 6 bladder biopsy documented persistent CIS or progression to the muscle invasive stage. Durvalumab will be discontinued and subjects will be off study if invasive bladder cancer (T1 or above) is documented in any of the bladder biopsies. Due to the nature of CIS of bladder, RECIST 1.1 or irRECIST will not be applicable to response assessment.

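### The off-study rules contradict each other: T1 at month 3 or 9 is off study under section 9 but not under the synopsis or section 3.1, and section 3.1 relies on an unscheduled month 18 biopsy

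*Combined protocol and SAP*

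**What the plan says.** Section 9 states: "Durvalumab will be discontinued and subjects will be off study if invasive bladder cancer (T1 or above) is documented in any of the bladder biopsies". Its one allowance is for persistent CIS at month 3, where dosing goes on to the month 6 biopsy.

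The synopsis (Study Design) takes patients off study for T2 or above at any biopsy. For CIS and T1 it uses a visit list: patients leave if their "month 6, 12, 16, 20, biopsies show persistent (month 6) or recurrent CIS or invasive (T1 or above) urothelial carcinoma". It then adds: "Otherwise, patients will remain on study until after the month 24 biopsy".

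Section 3.1 has the same T2 rule but a different list: "month 6, 12, 18 biopsies showed persistent (month 6) or recurrent CIS or invasive (T1 or above) urothelial carcinoma". It closes in the same way: "Otherwise, patient will remain on study until after the month 24 biopsy".

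The schedule of assessments puts surveillance cystoscopy at weeks "68, 86 104, (±14 days"). Footnote j names months 3, 9, 12, 16 and 20, with biopsy left to the urologist, besides the mapping biopsies at baseline, month 6 and month 24.

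Two further texts tie stopping for progression to the investigator's view of benefit. Section 5.1.2 has: "Study treatment should be discontinued prior to 12 months if there is confirmed PD (unless the investigator considers the subject to continue to receive benefit". The same sentence ends with a general clause covering any other ground for stopping. Section 4.3 item 9 lists as a ground for permanent discontinuation: "Confirmation of PD and investigator determination that the subject is no longer benefiting from treatment with durvalumab".

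The protocol does not define confirmed PD explicitly. Section 9 sets RECIST aside. Footnote k and section 9.1.1 point towards muscle invasion, while section 10.3 describes progression more broadly and includes new metastasis.

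**The concern.** Section 1.5 names the main hazard of the design: if the CIS does not respond, postponing cystectomy may let the disease become muscle invasive or metastatic. The off-study rule is the safeguard against that, and 2 to 3 centers have to apply it in the same way. A site working from the synopsis or section 3.1 would not learn that T1 at month 3 or 9 ends participation. Because both texts say that everyone not caught by the list stays on study, this is a contradiction and not merely a shorter statement of one rule.

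The same rule helps decide who is analysed. Section 11.1.2 requires at least 6 infusions and the month 6 mapping biopsy for the efficacy set. How a month 3 T1 finding is handled can therefore determine whether that subject is counted.

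**Working it through.** **Step 1. The texts side by side.**

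| Finding and visit | Section 9 | Synopsis | Section 3.1 |
|---|---|---|---|
| T2 or above, any biopsy | off | off | off |
| T1, month 3 or 9 | drug stopped, off | not listed, stays | not listed, stays |
| T1, month 6 or 12 | off | off | off |
| T1, month 16 or 20 | off | off | not listed, stays |
| Recurrent CIS, month 12 | not addressed | off | off |
| Recurrent CIS, month 16 or 20 | not addressed | off | not listed, stays |

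The any-biopsy conflict concerns T1 only; all three texts agree on T2. For recurrent CIS at months 16 and 20, section 9 gives no answer.

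**Step 2. Is month 18 a visit?** With week / 52 × 12, the surveillance weeks 68, 86 and 104 are months 15.7, 19.8 and 24.0. Month 18 is 18 / 12 × 52 = week 78. The nearest visit is week 86, which is 8 weeks away against a window of ±14 days. Only section 1.5, which speaks of 3-monthly cystoscopy over the 2 years, would produce a month 18 visit, and it disagrees with the synopsis and the schedule. On section 3.1's list, no scheduled visit falls between week 52 and week 104, a span of 104 − 52 = 52 weeks. Cystoscopies still take place at weeks 68 and 86.

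**Step 3. Infusions between the conflicting visits.** The dosing column runs 0, 4, ..., 48, which is 48 / 4 + 1 = 13 doses.

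- T1 at week 14: 4 doses given (weeks 0, 4, 8, 12). Before the next listed visit, week 26: weeks 16, 20, 24 = 3 infusions.
- T1 at week 38: before the next listed visit, week 52: weeks 40, 44, 48 = 3 infusions.
- Months 16 and 20: none, since dosing has ended.

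**Step 4. Analysis sets for a subject with T1 at week 14.**

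| Handling | Doses by week 26 | Efficacy set (6 or more doses and month 6 biopsy) | Intention-to-treat set (1 or more doses and month 6 biopsy) |
|---|---|---|---|
| Section 9, no further biopsy | 4 | out | out |
| Drug stopped, month 6 biopsy still done | 4 | out | in |
| On study and on drug | 4 + 3 = 7 | in | in |

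The second row is possible because section 6.1 follows subjects with fewer than 6 doses to the month 24 evaluation, and section 9.1.1 continues tumor assessment for those withdrawn from drug for reasons other than muscle-invasive progression. Section 9's off-study instruction points the other way.

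**Step 5. The design figures.** The stated type I error and power (0.0473 and 0.8031) reproduce by exact two-stage binomial enumeration with boundaries 3/13 and 9/34. Nothing in this point depends on them.

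**The case against.** The best defence is that a reader who follows every page stops the drug at T1. Section 9 is the only text that says what happens to durvalumab after T1, and it is unconditional. Neither the synopsis nor section 3.1 tells anyone to keep dosing; they speak only of study status. That stands, so the 3 infusions are a ceiling. It does not remove the contradiction about study status, and no text gives section 9 precedence.

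A reader might infer from section 5.1.2 that investigators may dose past muscle invasion. The documents do not support this. The exception qualifies only confirmed PD, the sentence closes with a clause for other grounds, and section 9's stop is such a ground. T2 is also covered unconditionally in the synopsis, footnote k and section 3.1. Section 4.3 item 9 authorises no dosing; it is one entry in a list of which any entry suffices. What remains is a poor fit of wording, which is a secondary point.

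A reader might also infer an inflated type I error, because subjects removed before month 6 are replaced. That effect belongs to the replacement rule in section 4.4 and needs a removal rate that the documents do not give. It does not measure this inconsistency. Nor is it certain that a subject stopped for T1 leaves the intention-to-treat set, for the reason shown under the second table.

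Month 18 can fairly be called a clerical leftover, since the synopsis, the schedule and footnote j agree on months 16 and 20. T1 and T2 at those visits are covered elsewhere. Recurrent CIS is not settled by section 9, and there section 3.1 and the synopsis give different answers.

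**Conclusion.** The point holds as a consistency defect in a safety rule and should be corrected. T1 at month 3 or 9 has two opposite study outcomes in current operative text. Recurrent CIS at month 16 or 20 also has two, because section 3.1 names a visit that does not exist. The benefit conditions in sections 5.1.2 and 4.3 item 9 add ambiguity but do not override the mandatory stops.

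The size is limited: up to 3 infusions per affected subject, assuming that a biopsy is taken at a visit where it is discretionary and that a site treats staying on study as staying on drug. A subject stopped for T1 at week 14 has 4 doses and is outside the efficacy set; whether the intention-to-treat set includes that subject depends on whether the month 6 biopsy is still done. The documents give no T1 or recurrence rates, so no number of patients is claimed. The Simon boundaries do not change.

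**What to change.** 1. In the synopsis and section 3.1, state the T1 rule as T1 or above at any biopsy.
2. In section 3.1, replace month 18 with months 16 and 20.
3. In section 5.1.2 delete the benefit exception, and in section 4.3 item 9 delete the no-benefit condition. In both, keep the term confirmed PD and add: *including T1 or above at any bladder biopsy, or CIS meeting the off-study rule*.
4. Keep section 9's allowance for persistent CIS at month 3.

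The term confirmed PD should be extended and not replaced. A trigger based on bladder biopsy alone could drop progression found elsewhere: section 10.3 counts new metastasis as progression, and section 9.1.2 recognises cancer outside the bladder.

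Recurrent CIS at month 9 is on neither visit list. Whether to add it is a clinical decision for the sponsor and is not part of this correction.

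The cost is one wording amendment in four places, with no new procedures or patients. Investigators lose discretion to continue dosing after documented progression.

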5.1.3 Study drug preparation

For patients weighing ≥ 30 kg, 1500 mg Q4W durvalumab (equivalent to 20 mg/kg Q4W) (based on an average body WT of 75 kg) should be prepared. For subjects <30 kg body weight, 20 mg/kg dose should be prepared; dose is determined using body mass, calculating the stock volume of durvalumab to achieve the accurate dose according to Appendix B.

Preparation of durvalumab doses for administration with an IV bag

The dose of durvalumab for administration must be prepared by the Investigator's or site's designated IP manager using aseptic technique. Total time from needle puncture of the durvalumab vial to the start of administration should not exceed:

- 24 hours at 2°C to 8°C (36°F to 46°F)
- 4 hours at room temperature

If in-use storage time exceeds these limits, a new dose must be prepared from new vials. Infusion solutions must be allowed to equilibrate to room temperature prior to commencement of administration.

No incompatibilities between durvalumab and polyvinylchloride or polyolefin IV bags have been observed. Dose of 1500mg durvalumab for patients >30 kg will be administered using an IV bag containing 0.9% (w/v) saline with a final durvalumab concentration ranging from 1 to 20 mg/mL, and delivered through an IV administration set with a 0.2- or 0.22- μ m in-line filter.

Remove a volume of IV solution from the IV bag equal to the calculated volume of durvalumab to be added to the IV bag prior to addition of durvalumab. Next, the volume of durvalumab (ie, 15.0 mL for 750 mg or 30.0 mL for 1500 mg of durvalumab) is added to the IV bag such that final concentration is within 1 to 20 mg/mL (IV bag volumes 100 to 1000 mL). Mix the bag by gently inverting to ensure homogeneity of the dose in the bag.

Patient weight at baseline should be used for dosing calculations in patients ≤ 30 kg unless there is a $\geq 10\%$ change in weight. Dosing day weight can be used for dosing calculations instead of baseline weight per institutional standard.

For patients <30 kg, calculate the dose volume of durvalumab and number of vials needed for the subject to achieve the accurate dose according to Appendix B.

Durvalumab will be administered at room temperature (approximately 25°C) by controlled infusion via an infusion pump into a peripheral or central vein. Following preparation of durvalumab, the entire contents of the IV bag should be administered as an IV infusion over approximately 60 minutes (± 5 minutes), using a 0.2, or $0.22\text{-}\mu\text{m}$ in-line filter. Less than 55 minutes is considered a deviation.

The IV line will be flushed with a volume of IV solution (0.9% [w/v] saline) equal to the priming volume of the infusion set used after the contents of the IV bag are fully administered, or complete the infusion according to institutional policy to ensure the full dose is administered and document if the line was not flushed.

Standard infusion time is 1 hour. However, if there are interruptions during infusion, the total allowed time should not exceed 8 hours at room temperature. The table below summarizes time allowances and temperatures.

Durvalumab hold and infusion times

Maximum time from needle puncture to start of administration	4 hours at room temperature, 24 hours at 2°C to 8°C
Maximum time for IV bag infusion, including interruptions	8 hours at room temperature

In the event that either preparation time or infusion time exceeds the time limits outlined above, a new dose must be prepared from new vials. Durvalumab does not contain preservatives, and any unused portion must be discarded.

